# Safety Endpoint Analysis

#### Safety Endpoint

The safety endpoint for this study is to assess the incidence and severity of cryoablation related adverse events.

#### **Analysis Methods**

Point estimates and two-sided Exact 95% confidence intervals will be generated for events related to the cryoablation procedure in the following categories:

- intra-operative events
- post-operative adverse events
- · serious adverse events
- unanticipated adverse device effects

The safety analysis will be performed on the ITT population. No formal statistical hypothesis testing will be performed for safety endpoints.

Confidential Page 4 of 9

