5.2. Safety Endpoints

The safety endpoint for this study is to assess the incidence and severity of cryoablation related adverse events.

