11. STATISTICAL ANALYSIS

11.1. General Methods

This is a prospective single-arm feasibility study designed to determine the safety of Galil Medical's Cryoablation System and needles in cryoablation of lung tumors, as well as give an insight into the efficacy of the treatment. This study is not powered for formal statistical analysis. All comparisons will be qualitative in nature. Descriptive results of this feasibility study may be used to generate hypotheses for a pivotal study.

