11.5.3. Safety Endpoints

The safety endpoint for this study is to assess the incidence and severity of intra-operative events, post operative adverse events, serious adverse events and unanticipated adverse device effects related to the cryoablation procedure.

Point estimates and two-sided 95% confidence intervals will be generated for cryoablation related adverse events.

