14. SAFETY ASSESSMENTS

All adverse events (AEs), serious adverse events (SAEs) and unanticipated adverse device effects (UADEs) that occur within 30 days after the cryoablation procedure is performed will be recorded. The AEs, SAEs and UADEs identified within the first 30 days after the cryoablation procedure will be followed and reported until resolution or for a period of 6 months.

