14.2. Causality Assessment

The investigator's assessment of causality must be provided for all adverse events (serious and non-serious). An investigator's causality assessment is the determination of whether there exists a reasonable possibility that the procedure or study device caused or contributed to an adverse event. If the investigator's final determination of causality is unknown and the investigator does not know whether or not the procedure or study device caused the event, then the event will be handled as "related to procedure or study device" for reporting purposes. If the investigator's causality assessment is "unknown but not related to procedure or study device", this should be clearly documented on study records.

The investigator will evaluate AEs/SAEs/UADEs using the following guidelines:

- Description of event (if the event consists of multiple signs and symptoms, a diagnosis should be recorded rather than each sign and symptom)
 - Record term and grade according to the CTCAE grading criteria
- Onset Date
- Stop Date
- Seriousness
 - The investigator must determine whether or not the AE meets the definition of serious as noted above and record in the eCRF. If the event is serious, the investigator must inform the Sponsor within 24 hours of knowledge of the event and complete the SAE report form.
- Relationship to Study Procedure or Study Device
 - The investigator must make a causality assessment for all AEs and decide whether there is a reasonable possibility the AE was caused by the procedure or study device.
 - If there is a valid reason to suspect a causal relationship between the AE and the procedure or study device, the AE should be considered "related or possibly related" to the procedure or study device.
- Outcome
- Action Taken

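### The planned adverse-event rates count only events attributed to the procedure; all 30-day events are collected, but no all-cause AE or SAE rate is planned beside them

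*SAP*

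**What the plan says.** **Endpoint.** Protocol 5.2 reads "The safety endpoint for this study is to assess the incidence and severity of cryoablation related adverse events". The SAP's Safety Endpoint paragraph uses the same restriction.

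**Analysis.** Protocol 11.5.3 states "Point estimates and two-sided 95% confidence intervals will be generated for cryoablation related adverse events". The SAP's Analysis Methods under Safety Endpoint Analysis plans exact 95% intervals for "events related to the cryoablation procedure in the following categories", and lists intra-operative events, post-operative AEs, SAEs and UADEs.

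**Collection.** Protocol section 14 covers AEs, SAEs and UADEs "that occur within 30 days after the cryoablation procedure is performed will be recorded". The AE definition in 14.1 does not depend on relatedness.

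**Attribution.** Protocol 14.2 says "The investigator must make a causality assessment for all AEs". A reasonable possibility is enough for an event to be called related or possibly related. An event whose cause the investigator does not know is handled as related for reporting purposes. The SAP (Randomization and Blinding) confirms that nobody is blinded.

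**Purpose.** Protocol 11.1 describes the study as "designed to determine the safety of Galil Medical's Cryoablation System and needles".

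**The concern.** With no control arm, attribution is the only step between the events recorded and the safety rates reported, and one unblinded person's judgement decides it for each event. The patients have Stage 4 disease. Protocol Appendix B lists dyspnea, lung infection, atrial fibrillation, thromboembolic event and myocardial infarction among the anticipated procedure-related events. Any of these could also plausibly come from the disease or from comorbidity. If such an event is non-fatal and is put down to the disease, it stays in the database but enters no specified AE or SAE rate.

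Two things are at stake. A reader of the planned output cannot see how much of the safety result depends on attribution, because the exact interval reflects sampling error only. And the protocol (11.2) and SAP (Sample Size Justification) intend these estimates to inform the decision on a pivotal study and its design. With 30 to 40 patients, one or two attributions move a rate visibly.

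**Working it through.** The documents give no expected safety rate, so there is no planned figure to reproduce. The check is a reading of the text, followed by an illustration.

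**1. What is collected against what is summarised**

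| Item | Collected | Planned summary |
|---|---|---|
| Non-fatal 30-day AE or SAE, judged related | Yes (Protocol 14, 14.1) | Rate with exact 95% CI (SAP, Safety Endpoint Analysis) |
| Non-fatal 30-day AE or SAE, cause unknown | Yes | Handled as related for reporting (Protocol 14.2); the SAP does not say whether this carries into the analysis |
| Non-fatal 30-day AE or SAE, judged unrelated | Yes | No AE or SAE rate named |
| Death from any cause | Yes | Kaplan-Meier overall survival (Protocol 11.5.4; SAP, Disease recurrence or progression) and death count (SAP, Subject Disposition) |
| Chest tube placement | Yes | Summarised with no attribution filter (SAP, Intra-procedural data) |

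The SAP's Additional Data Summaries do not list adverse events. Its General Analysis Methods paragraph is generic and names no all-cause AE or SAE table. The gap is the third row.

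**2. Direction**

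For the same window, denominator and event category, patients with a related event are a subset of patients with any event. So the related rate is at most the all-cause rate. This needs the window to match. The SAP states none; Protocol 14 limits recording to 30 days, while Protocol Table 1 schedules safety assessments to Month 60.

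**3. Size (illustration)**

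Inputs: n = 35 is an assumption inside the planned 30 to 40, and all event counts are assumptions. The interval is Clopper-Pearson, as an exact interval for a proportion. For x of n patients:

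- lower limit = Beta quantile at 0.025 with parameters (x, n - x + 1)
- upper limit = Beta quantile at 0.975 with parameters (x + 1, n - x)

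| Patients with an SAE, any cause | Judged related | All-cause rate (95% CI) | Related rate (95% CI) | Ratio |
|---|---|---|---|---|
| 3 | 1 | 3/35 = 8.6% (1.8-23.1%) | 1/35 = 2.9% (0.1-14.9%) | 3/1 = 3.0 |
| 5 | 3 | 5/35 = 14.3% (4.8-30.3%) | 3/35 = 8.6% (1.8-23.1%) | 5/3 = 1.7 |

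In the first row the upper limit falls by 23.1 - 14.9 = 8.2 points; in the second by 30.3 - 23.1 = 7.2 points.

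The 3-against-1 case at the ends of the planned range:

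- n = 30: 10.0% (2.1-26.5%) against 3.3% (0.1-17.2%)
- n = 40: 7.5% (1.6-20.4%) against 2.5% (0.1-13.2%)

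The threefold ratio belongs to 3 falling to 1. It is not a general size of the effect.

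**The case against.** The other side has a good deal of substance.

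- **The endpoint is consistent.** Protocol 5.2 and 11.5.3 and both SAP safety paragraphs specify related events. A reader might infer that the SAP departs from the protocol; it does not. This stands.
- **Unrelated events do not vanish altogether.** A reader might infer that an event judged unrelated appears in no rate at all. That is wrong for deaths, which enter overall survival and the disposition count whatever their cause. The gap is confined to non-fatal events.
- **The four categories are not equally exposed.** Protocol 14.1 defines a UADE as caused by or associated with the device, so the related filter is largely built in. Intra-operative events leave less room to blame background disease. Post-operative AEs and SAEs carry the point.
- **Attribution is not loose.** The reasonable-possibility threshold and the handling of unknown cause as related both limit under-attribution. Neither helps once the investigator decides that an event is unrelated. The independent Medical Monitor (Protocol 17.1) reviews safety data but has no stated role in attribution.
- **The assessor's role.** It is tempting to say that the physician who performed the ablation judges its complications. Protocol 14.2 says only the investigator.
- **No decision rule is affected.** The study is descriptive, with no hypothesis test and no stated safety threshold. The intervals in the illustration overlap heavily. The relationship assessment is recorded for every AE, so an all-cause table could be produced later without loss of data. This limits the severity. It does not supply a pre-specified all-cause rate.

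**Conclusion.** The point holds as an improvement to the plan, not as an error in it. Every planned adverse-event rate depends on the unblinded investigator's attribution, and no all-cause AE or SAE rate is planned although the 30-day data are collected. The consequence is limited to non-fatal events judged unrelated, chiefly post-operative AEs and SAEs.

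The size cannot be known in advance. On the assumed counts, two attributions divide the SAE rate by between 1.7 and 3 and lower its upper limit by 7 to 8 points at n = 35. The documents give no basis for saying that under-attribution will occur, or that it would reverse a decision to go on to a pivotal study. They do show that the planned output would not let a reader see it.

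**What to change.** In the SAP, Safety Endpoint Analysis, Analysis Methods:

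1. Keep the related-event rates as the endpoint.
2. Add beside them, with exact 95% intervals, the proportion of treated patients with at least one 30-day post-operative AE and the proportion with at least one 30-day SAE, regardless of relationship.
3. Use the same 30-day window and the patient as denominator for both the related and the all-cause rates. The SAP now states neither window nor denominator. Bilateral treatment falls on separate days (Protocol 7.2.4), so also say which procedure starts the window.
4. Count unknown causality as related in the related rates, in line with Protocol 14.2.

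The cost is a few table rows from data already in the database, with no change to endpoint, sample size or procedures. The downside is that the all-cause figures will be as high as or higher than the related ones and will include some background disease events. Showing the two side by side makes that difference visible.

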# Supportive Endpoint Analyses

#### Technically successful treatment

A technically successful treatment will be defined by an ablation volume encompassing the tumor with at least a 5 mm margin. Technical success will be calculated on a per tumor level as well as a patient level. To be considered a technical success on a patient level all tumors treated during the baseline procedure must meet the technical success criteria.

#### Disease recurrence or progression

Disease specific survival, overall survival, and time to disease recurrence or progression will be analyzed by Kaplan-Meier methodology. These measures are defined as:

**Disease-specific survival** will be analyzed as the time in days from cryoablation procedure to death due to lung cancer. Patients who are alive will be censored at the date of their last visit. Patients who have died from causes other than lung cancer will be censored at the time of death.

**Overall survival** will be analyzed as the time in days from cryoablation procedure to death. Patients who are alive will be censored at the date of the last visit.

Freedom from disease recurrence or progression will be analyzed as the time in days from cryoablation procedure to disease recurrence or progression, determined locally by evidence of an increase in tumor size and/or contrast enhancement. Patients without disease recurrence or progression will be censored at the date of their last visit or their date of death (due to any cause).

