8. STUDY PROCEDURES

The study schedule of events and the specific procedures performed at each visit are shown in Table 1, Schedule of Events. Each patient will undergo a total of 11 visits, including an initial/screening visit, the procedure visit, and 9 post-operative visits. The Month 1 post-operative visit may be a telephone visit or a clinic visit. More visits may be required when medically necessary.

Table 1: Schedule of Study Events

Procedures	Screening	Procedure Date	W 1ª	M 1 ^b	M 3, 6 & 12 d	M 24, 36, 48, 60 ^e or Withdrawal
Informed Consent	Х					
Inclusion/Exclusion	Х					
Demographics	Х					
Targeted Medical History	х					
ECOG & Karnofsky	Х		Х	Χ°	Х	Х
Pertinent Medication	Х		Х	Х		
Discontinue anticoagulation, as clinically indicated	х					
CT/MRI Scan ^f	Х		Χg		Х	Х
Record tumor characteristics	х					
Chest X-Ray			Χg			
Cryoablation procedure		Х				
Labs h	Х					
Quality of Life (SF-12) i	Х			X	Х	х
Safety Assessments		Х	Х	Х	Х	Х

^aWeek 1 visit within +/- 7 days of cryoablation procedure

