8.1. Screening

The screening period begins after written informed consent has been obtained. The screening visit allows the investigator to assess a patient's eligibility for this study.

CUC10-LNG06-04 Page 13 of 38

b Month 1 visit may be done by telephone interview or clinic visit. Visit window +21/-7 days

Complete only if a Clinic Visit

d Months 3, 6 and 12 visit window +45 days

e Months 24, 36, 48 and 60 visit window +90 days

f CT/MRI scan with contrast for follow-up at 3 months, 6 months, 1 year then yearly per routine post treatment f/u

Week 1 imaging may be a CT, MRI or X-Ray with or without contrast

h Platelet Count, ANC and INR – within 60 days of study procedure

ⁱTo be completed before treatment starts then at 1, 3, 6, 12, 24, 36, 48 and 60 months post cryoablation

The following assessments will be completed during screening and within 6 weeks of the cryoablation procedure:

- Informed consent;
- Review inclusion/exclusion criteria;
- Patient number assigned;
- Demography;
- Targeted medical history, including comorbidities;
- ECOG:
- Karnofsky Performance Scale;
- Baseline labs (Platelet Count, ANC and INR);
- CT/MRI scan of chest with contrast to include lungs, liver, and adrenal glands;
- Tumor characteristics (See Section 5.4);
- Quality of Life assessments (SF-12);
- Current pertinent concomitant medication;
- Discontinue anticoagulation as clinically indicated;
- Assess for clinical safety of General Anesthesia (if applicable).

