8.5. Months 3, 6 and 12 - Follow-up

Patients will return 3, 6 and 12 Months (+/-45 days) post cryoablation procedure to complete the following assessments:

- ECOG:
- Karnofsky Performance Scale;
- Quality of Life assessments (SF-12);
- CT/MRI Scan, with contrast;
- Safety assessments;
- Assessment of disease progression, including retreatment;
- Assess any new cancer treatment(s).

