8.6. Months 24, 36, 48, 60 and Study Completion or Withdrawal

Patients will return 24, 36, 48 and 60 months (+/- 90 days) post cryoablation procedure or at Study Withdrawal and complete the following assessments:

- ECOG;
- Karnofsky Performance Scale;
- Quality of Life assessments (SF-12);
- CT/MRI Scan, with contrast:
- Safety assessments;
- Assessment of disease progression, including retreatment;
- Assess any new cancer treatment(s).

Patients who request Early Termination from the study will be asked to return for a final visit to complete the above assessments.

Patients may be considered "lost to follow-up" after 3 unsuccessful attempts to contact the patient with on contact being a registered letter to the last known address of the patient. Site should document all attempts to contact the patient in the source documents.

CUC10-LNG06-04 Page 16 of 38

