9.6. Computed Tomography (CT) and Magnetic Resonance Imaging (MRI)

As outlined in this protocol, all patients will have an initial CT or MRI prior to therapy. The cryoablation procedure will be completed under CT guidance only. Follow-up imaging at Week 1 will be either CT, MRI or X-Ray. At Months 3, 6, 12, 24, 36, 48 and 60, follow up imaging will be CT or MRI with contrast unless contrast is contraindicated.

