11.5.4. Other Endpoints

Technically successful treatment definition

A technically successful treatment will be defined by an ablation volume encompassing the tumor with at least a 5 mm margin.

Technical success will be calculated on a per tumor level as well as a patient level. To be considered a technical success on a patient level all tumors treated during the baseline procedure must meet the technical success criteria.

Disease recurrence or progression definitions

Disease recurrence or progression will be determined locally by evidence of an increase in tumor size and/or contrast enhancement.

Disease-specific survival rate is defined as the time in days from cryoablation procedure to death due to lung cancer. Patients who are alive will be censored at the date of their last visit. Patients who have died from causes other than lung cancer will be censored at the time of death. Disease-specific survival rates will be summarized by using Kaplan-Meier methodology.

Overall survival rate is defined as the time in days from cryoablation procedure to death. Patients who are alive will be censored at the date of the last visit. Overall survival rates will be summarized by using Kaplan-Meier methodology.

Time to recurrence is defined as the time in days from cryoablation procedure to disease recurrence or progression. Patients without disease recurrence or progression will be censored at the date of their last visit or their date of death (due to any cause). Recurrence free survival rates will be summarized by using Kaplan-Meier methodology.

Intra-procedural data

Initial cryoablation procedure information including the type of procedure, tumor size and number, cryoablation needle type and the number of each type of needle used, freeze and thaw times, method of thaw (active or passive), and ice formation and how it encompasses the tumor will be summarized.

Physical performance and quality of life

Physical performance (ECOG and KPS) and quality of life (SF-12) assessments will be made by examining the change in the baseline scores to those reported post-operatively as defined in Sections 9.3.1 and 9.5, respectively.

CUC10-LNG06-04 Page 20 of 38

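### Recurrence is judged mainly on scans that become a year apart, but its time is analysed by ordinary Kaplan-Meier in days; if the scan date is the event date, freedom from recurrence is overstated by an assumption-dependent amount

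*SAP*

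**What the plan says.** The SAP, under Disease recurrence or progression, states: "Disease specific survival, overall survival, and time to disease recurrence or progression will be analyzed by Kaplan-Meier methodology". Protocol 11.5.4 gives the time scale: "Time to recurrence is defined as the time in days from cryoablation procedure to disease recurrence or progression". Both documents censor patients without recurrence at their last visit or at death from any cause.

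Recurrence or progression is "determined locally by evidence of an increase in tumor size and/or contrast enhancement" (SAP, same section), so it rests on imaging. Protocol 9.6 sets the imaging times: "At Months 3, 6, 12, 24, 36, 48 and 60, follow up imaging will be CT or MRI with contrast unless contrast is contraindicated". The footnote to Table 1 agrees: "CT/MRI scan with contrast for follow-up at 3 months, 6 months, 1 year then yearly per routine post treatment f/u".

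The windows are in Protocol 8.5, "Patients will return 3, 6 and 12 Months (+/-45 days) post cryoablation procedure", and 8.6, "Patients will return 24, 36, 48 and 60 months (+/- 90 days) post cryoablation procedure".

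Neither document says which date counts as the recurrence date, names a method for interval-censored data, ties scans to scheduled visits for this analysis, or says at which times the recurrence curve will be read.

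**The concern.** A recurrence found on a scan began at some unknown time after the last clear scan. A scan cannot precede the recurrence it shows, so dating the event at the scan can only move it later. The curve then stays flat between scan rounds and drops as the scans are done. At a nominal date such as 24 months, about half of the Month 24 scans may still be outstanding, and the recurrences they would show are not yet counted.

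The censoring rule adds to this. A patient who dies 11 months after a clear scan is counted as recurrence-free for those 11 unobserved months. A last visit is also not always a scan, since the Month 1 visit may be a telephone call.

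The study is descriptive, so its estimates are its product, and the SAP's Sample Size Justification says that they will be used to power a pivotal study. A durability figure that errs in one direction, by an amount that depends on how late patients attend, is a poor basis for that.

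**Working it through.** The plan gives no recurrence rate or precision figure for this endpoint, so there is nothing to reproduce. The check asks how large the bias would be.

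**Inputs from the documents.** Scans at Months 3, 6, 12, 24, 36, 48 and 60; windows ±45 days (1.48 months) to Month 12 and ±90 days (2.96 months) afterwards; 30 to 40 patients. The Table 1 footnotes show the windows as +45 and +90, which may be a loss in reading the PDF; the section text is used here.

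**Assumptions, not in the documents.** Constant recurrence hazard λ = ln 2 / median, with medians of 1.0 to 3.1 years (3.1 years is 20% per year: 0.693/0.223). Scan dates uniform within the windows. Event date equal to the positive-scan date. No off-schedule imaging. For orientation, the metastasis series in Protocol 3.2 reports 54.3% recurrence with 21 months' median follow-up. Taken as a 21-month risk, this gives λ = −ln(0.457)/21 = 0.0373 per month, a median of 18.6 months (1.55 years).

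**1. Width of the interval.** Two consecutive yearly scans can be 12 months + 90 days + 90 days apart, about 18 months.

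**2. Scans exactly on time, death unrelated to recurrence.** The Kaplan-Meier value at t is S(last scan at or before t), so the bias is S(last scan) − S(t). It is zero at every scan month. At Month 18 it is 0.80 − 0.80^1.5 = 8.4 points at 20% per year and 0.65 − 0.65^1.5 = 12.6 points at 35% per year. Just before the Month 24 scan at 20% per year it is 0.80 − 0.64 = 16 points.

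**3. Scans spread over the windows, death unrelated to recurrence.** At nominal Month 24, half of the patients were last scanned in the Month 12 window and half have had the Month 24 scan. So KM(24) = ½·A + ½·B, where A is the mean of S over 12 ± 1.48 months and B is the mean of S over 21.04 to 24 months. For a median of 1.5 years, λ = 0.0385 per month, A = 0.630, B = 0.420, KM(24) = 0.525 and S(24) = 0.397. The bias is 12.8 points. The same formula gives:

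| True median (years) | Month 12: true / KM | Month 24: true / KM | Month 36: true / KM | Bias (points) |
|---|---|---|---|---|
| 1.0 | 50.0 / 61.5 | 25.0 / 38.7 | 12.5 / 19.4 | 11.5, 13.7, 6.9 |
| 1.5 | 63.0 / 72.1 | 39.7 / 52.5 | 25.0 / 33.1 | 9.1, 12.8, 8.1 |
| 2.5 | 75.8 / 82.1 | 57.4 / 67.6 | 43.5 / 51.3 | 6.3, 10.2, 7.7 |
| 3.1 | 80.0 / 85.3 | 63.9 / 72.9 | 51.1 / 58.3 | 5.3, 8.9, 7.1 |

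The range is about 5 to 14 points. Simulation agrees.

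**4. Median.** Solving KM(t) = 0.5 with the same formula, true medians of 1.0, 1.5, 2.0 and 2.5 years are estimated as 1.76, 2.05, 2.76 and 3.04 years, which is 0.76, 0.55, 0.76 and 0.54 years late.

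**5. Death more likely after recurrence.** Simulation with assumed death hazards of 0.1 per year before and 0.5 per year after recurrence gives, at Month 24, 42% against a true 25% (median 1.0 year), 56% against 40% (1.5 years) and 70% against 57% (2.5 years). The largest bias is about 17 points. With equal hazards of 0.1, simulated bias falls to 13.7, 12.5 and 10.4 points, so about 2 to 3 points at this reading time come from the assumed excess deaths.

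**6. Do the remedies work?** Over 400 simulated trials of 40 patients without deaths, read at Months 12 to 36, Turnbull bias ran from −0.4 to +1.8 points, against +5.0 to +13.3 for Kaplan-Meier. Reading Kaplan-Meier at the end of the Month 24 window gives the mean of S over 24 ± 2.96 months, 39.8% against 39.7% for a median of 1.5 years. With the excess deaths of step 5, both remedies still give about 45% against 40%.

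**The case against.** The strongest reply is that no particular bias is a property of this plan. A reader might infer a fixed overstatement of some 7 to 17 points. The documents give no recurrence rate, death rate or attendance pattern, and the upper end needs an assumed five-fold higher death hazard after recurrence. Under punctual scanning the bias at the scan months is nil. This stands, and the size can only be stated as a range.

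A reader might also infer that the SAP prescribes the scan date as the event date. It does not; the date is undefined. Scan dating is the natural outcome of the text, but it is an inference. Nor do the documents say that recurrence can be seen only at the yearly scans. Protocol 8 says "More visits may be required when medically necessary", and 8.6 requires CT/MRI at withdrawal, which under 6.2 follows when an index tumor needs further local treatment. Off-schedule imaging would shrink the bias, and the calculations above leave it out.

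The reading time also matters. Protocol 5.3 lists follow-up months for disease-specific survival but none for recurrence. Read at the end of each visit window, the rates are essentially unbiased unless deaths depend on recurrence. That does not rescue the median or the curve between scans.

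Finally, the endpoint is supportive, no tests are planned, and the simulated standard error with 40 patients is about 6 to 8 points, of the same order as the bias. That limits the importance. But sampling error has no preferred direction and shrinks with more patients; this bias does neither.

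**Conclusion.** The concern holds as a matter of method. Imaging is sparse after Month 12, the analysis is ordinary Kaplan-Meier in days with no interval-censoring provision, and censoring is at last visit or death instead of last scan. If the positive-scan date is the event date, freedom from recurrence and its median are biased upward.

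The size is conditional. It is zero at scan months with punctual scans and death unrelated to recurrence; about 5 to 14 points at nominal Months 12 to 36 with uniform scan dates in the ± windows and true medians of 1.0 to 3.1 years; and up to about 17 points if death is also much more likely after recurrence. The median is late by about 0.5 to 0.75 years for true medians of 1.0 to 2.5 years. All of this assumes a constant hazard and no off-schedule scans.

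A reader should not extend this to the efficacy endpoint. Local control is a proportion at each visit and does not use Kaplan-Meier event dates. The change is worth making, but the study does not depend on it.

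**What to change.** In the SAP section on disease recurrence or progression, and in Protocol 11.5.4:

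- Define the recurrence interval as running from the last CT/MRI without recurrence to the first CT/MRI with it, counting unscheduled and withdrawal scans.
- Right-censor patients without recurrence at their last CT/MRI, not at last visit or death.
- Use an interval-censored (Turnbull) estimate. Alternatively, assign scans to scheduled visits and report rates only at the end of each visit window.
- State that recurrences never imaged before death leave a residual bias that neither option fully removes.
- Keep Kaplan-Meier for overall and disease-specific survival.

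The cost is SAP wording, a little programming and less favourable recurrence-free figures. The Turnbull estimate is also somewhat less precise: at Month 24 with 40 patients and 20% recurrence per year, its simulated standard deviation was 8.5 points against 6.9 for Kaplan-Meier.
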